10.1.2. Sensitivity Analyses

Sensitivity analyses will include the assessment of the contribution of interaction terms and effect modification analyses.

The following sensitivity analyses will be performed by [REDACTED]

- For each of the primary comparisons, an analysis of variance model will be fit that adds an arm-by-BMI interaction term to the model. That is, the sensitivity model will include treatment arm, BMI class, arm-by-BMI-class interaction, and a covariate of baseline cigarettes. If there is evidence of an interaction then each of the primary comparisons will be repeated within each level of the BMI class variable.
- The placebo treatment arms (Placebo – Commercial Schedule, Placebo – tid Schedule) will be compared using an analysis of variance model with fixed effects for treatment arm (2 levels) and BMI class (3 levels) and a covariate of baseline cigarettes. The Least Square (LS) Means, LS Means Differences, and their respective 95% CIs will be reported.
- If the placebo treatment arms are similar then the primary efficacy analysis will be repeated using the pooled placebo arms. The sensitivity analysis described in the previous paragraph will also be repeated.

Additional sensitivity analyses for the primary comparisons will be conducted by an independent statistician ([REDACTED]). These include a sensitivity analysis that computes the standard error (SE) for each subject of the cigarette-count data collected post-randomization and uses $1/(SE^2)$ as a weight.

Exploratory analyses will also be conducted by [REDACTED] as described below in order to identify effect modifiers. The objective of these analyses is to assess the homogeneity of treatment effect within strata (subgroups) defined by each potential effect-modifying variable. Strata for continuous effect modifiers will be defined by either logical considerations (e.g., age >65 years) or statistical criteria (e.g., quantile (median, tertile) split). The variables (factors) that will be evaluated as effect modifiers include, but are not limited to:

- demographic characteristics (e.g., sex, age, race, BMI),
- smoking history variables (e.g., duration of smoking, average number of cigarettes the subject reported smoking per day over the past 30 days, number of previous quit attempts),
- baseline smoking variables (e.g. average number of cigarettes smoked per day over 7 consecutive days as reported in the subject diary, baseline CO (ppm)),
- baseline questionnaire scores (see [Section 8.6](#)),
- clinical site.

Each factor will be evaluated in a two-arm analysis of variance model with fixed effect terms for treatment arm (experimental arm, control arm), the factor, and arm-by-factor interaction, and the covariate of baseline cigarettes. The following summary statistics will be reported for each level of a factor: the number of subjects overall and within each treatment arm, the mean difference between treatment arms in the primary endpoint (percent of expected cigarettes smoked), and the 95% CI for the difference. Forest plots will be used to display the 95% CIs for all factors.

The sensitivity analyses described above will be repeated using an analysis of variance model that does not include the covariate of baseline cigarettes, and for models with BMI class as a stratifier and without BMI as a stratifier.

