Regarding preliminary pharmacodynamic results, although smokers in the study were not required to have a designated or predetermined quit date, subjects overall in the trial had a significant reduction in number of daily cigarettes smoked by the end of treatment (Figure 1). Mean baseline cigarette consumption in this 18 to 65 year age group was 16.25 (\pm 3.5) cigarettes per day with exhaled CO of 19.9 (\pm 7.3) ppm. By the end of treatment on Day 25, subjects in the 1.5 mg cytisine treatment group were smoking only 8% of the cigarettes compared to baseline cigarette smoking (i.e. a 92% reduction in daily cigarette smoking). Subjects in the 3.0 mg cytisine treatment group were smoking only 5% of the cigarettes compared to baseline cigarette smoking (i.e. a 95% reduction in daily cigarette smoking).

Figure 1: ACH-CYT-02: Percent of Cigarettes Smoked Daily During Study Treatment Compared to Baseline Number of Cigarettes Smoked (N=24)

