4. EFFICACY AND SAFETY ENDPOINTS

4.1. Efficacy Endpoints

Efficacy endpoints will be based on cigarette consumption data. Subjects will record their cigarette consumption in a daily diary for 7 consecutive days during the screening period, and each day during the 25-day treatment period (i.e. on Day 1 through Day 25, inclusive). After Day 25, subjects will attend a Day 27 End of Treatment (EOT) clinic visit and post-treatment follow-up visits at Week 5, Week 6, Week 7 and Week 8. At each visit clinic staff will ask subjects whether they have smoked since the previous clinic visit and/or over the past 7 days, and the number of cigarettes smoked in the past 7 days.

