4.1.1. Primary Efficacy Endpoint

The primary efficacy endpoint will be based on the daily cigarette consumption data recorded in the subject diary. The primary efficacy endpoint is defined as the percent of expected cigarettes smoked computed for each subject, at end of treatment. This percent is designated by Y, Y is calculated as below:

$$Y = \frac{100 \times N}{T \times R}$$

where N represents total number of cigarettes smoked each day over the treatment period from Day 1 to Day 25; T represents number of post-randomization days where number of cigarettes smoked is recorded; and R represents the average number of cigarettes smoked daily over the 7-day screening period as baseline. T*R represents the total number of cigarettes that would have been smoked without intervention over the number of recorded days.

If a subject has no cigarette-count data collected post-randomization, then the primary endpoint will be imputed to a value of 100 (i.e., no change from baseline cigarette consumption). This is equivalent to imputing the total number of post-randomization days with data recorded (T) is 25 and the total number of cigarettes smoked over the treatment period (N) is the average number smoked daily at baseline (R) times 25.

The primary comparisons for this endpoint will be comparisons of active arms to the associated placebo arm, refer to [Figure 1](#):

Arm A (1.5 mg cytosine commercial schedule) versus Arm C (placebo commercial schedule),
Arm B (3.0 mg cytosine commercial schedule) versus Arm C (placebo commercial schedule),
Arm D (1.5 mg cytosine tid schedule) versus Arm F (placebo tid schedule), and
Arm E (3.0 mg cytosine tid schedule) versus Arm F (placebo tid schedule).

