10. EFFICACY ANALYSIS

The efficacy analyses will be conducted using subjects in the All Randomized Analysis Set, as defined in [Section 6.4](#). Subjects will be evaluated by their randomized treatment arm ('intent-to-treat' analysis).

For qualitative endpoints, summary tables will present the number and percentage of subjects for each class of the endpoint. Quantitative endpoints will be summarized by presenting the mean, SD, minimum, median and maximum values. All summary statistics will be presented by treatment arm.

The planned figures for efficacy endpoints are displayed in [Section 15](#).

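### The planned 1/SE² sensitivity analysis weights each subject by the spread of their own cigarette counts, so the weight depends on the response and does not exist for some randomized subjects

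*SAP*

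**What the plan says.** The primary endpoint in SAP 4.1.1 is Y = 100·N/(T·R). N is the total of the daily counts over Days 1 to 25, R is the screening daily average, and "T represents number of post-randomization days where number of cigarettes smoked is recorded". For empty diaries the section adds: "If a subject has no cigarette-count data collected post-randomization, then the primary endpoint will be imputed to a value of 100".

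SAP 10.1.1 analyses Y with an unweighted model. SAP 10.1.2 then assigns further sensitivity analyses of the primary comparisons to an independent statistician. One of them "computes the standard error (SE) for each subject of the cigarette-count data collected post-randomization" and "uses $1/(SE^2)$ as a weight". No formula for the SE is given, and no scale, floor, cap or rule for an SE that is zero or cannot be computed.

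SAP 10 states: "The efficacy analyses will be conducted using subjects in the All Randomized Analysis Set". Later in 10.1.2: "The sensitivity analyses described above will be repeated using an analysis of variance model that does not include the covariate of baseline cigarettes". The same sentence also calls for models with and without BMI class.

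In Protocol 7.2 (footnotes to Tables 8 and 9), the quit date falls on one of treatment Days 5 to 7.

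**The concern.** Inverse-variance weighting makes sense when the SE measures the sampling error of the value being weighted. Here it does not. With a complete 25-day diary, Y is fully observed, and day-to-day spread is not error in Y. A subject who smokes at baseline and then stops on the quit date has a large spread because the quit attempt worked.

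Three faults follow:

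- **Response-dependent weight.** The weight and Y are functions of the same counts. Abrupt quitters are down-weighted, and subjects near zero from Day 1 are strongly up-weighted.
- **Mismatched scale.** The SE is in cigarettes and Y is a percentage of baseline, so the same relative pattern counts for less in a heavier smoker.
- **Undefined weights.** A constant diary, including all zeros, has SE = 0. A one-day diary has no sample SE. An empty diary has no counts, and filling it with R on every day, as SAP 4.1.1 describes, gives SE = 0 again.

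A difference from the primary result could not be read as lack of robustness, and agreement could not be read as robustness. If all-zero diaries were dropped because their weight is infinite, the best responders would leave the analysis.

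**Working it through.** **The plan's own figure.** The SAP states nothing for the weighted analysis. Its precision figure for the unweighted comparison (SAP 3.5: SD 17, 50 vs 25) reproduces: t(0.975, 73 df) × 17 × √(1/50 + 1/25) = 1.993 × 17 × 0.2449 = 8.30, against the stated ±8.3. It serves below as a yardstick.

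**Inputs.** From the documents: 25 diary days; quit on Day 5, 6 or 7; entry minimum 10/day (Protocol 8.1); and, from Protocol 4.1, "Mean baseline cigarette consumption in this 18 to 65 year age group was 16.25" cigarettes per day. Assumed: SE = SD/√T, and a within-subject daily SD of 1 to 4 for a steady smoker, since the documents give none.

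**Weight.** 1/SE² = T/SD².

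- *Abrupt quitter*, 16.25 on Days 1–5, then 0: mean 3.25; SD² = (5 × 13² + 20 × 3.25²)/24 = 44.0; SD 6.634; SE 1.327; weight 25/44.0 = 0.568.
- *Steady smoker*, SD 1, 2, 4: weights 25, 6.25, 1.56.
- *24 zero days and one cigarette*: SD 0.2; SE 0.04; weight 625. This is twice the total weight of 50 steady smokers with SD 2 (50 × 6.25 = 312.5).
- *Scale*: five days at baseline, then zero, gives weight 1.5 at 10/day and 0.375 at 20/day. Y is 20 in both.

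**Steady smoker's weight divided by the quitter's, at 16.25/day**

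| Steady SD | Quit Day 5 | Day 6 | Day 7 |
|---|---|---|---|
| 1 | 37.0 | 44.0 | 50.2 |
| 2 | 9.2 | 11.0 | 12.5 |
| 4 | 2.3 | 2.8 | 3.1 |

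At 10/day the range is 0.88 (SD 4, Day 5) to 19.0 (SD 1, Day 7).

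**Effect on the estimate: hand check.** Assume quit/halve/continue proportions of 40/40/20 on active and 15/45/40 on placebo, quit Day 6, SD 2. The Y values are 20, 60 and 100.

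- Unweighted means: 0.40×20 + 0.40×60 + 0.20×100 = 52, and 0.15×20 + 0.45×60 + 0.40×100 = 70. Difference -18.
- Approximate weights: 0.568; 25/(44.0/4 + 4) = 1.67; 6.25.
- Weighted means: 169.5/2.144 = 79.1 and 296.7/3.335 = 89.0. Difference about -9.9.

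**Simulation.** 2000 trials, 50 vs 25, baseline normal with mean 16.25 and SD 3.5 floored at 10, quit Day 5–7, complete diaries, weighted arm means without covariates:

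| Pattern | Daily SD | Unweighted | Weighted |
|---|---|---|---|
| Abrupt quitting, mix as above | 1 | -18.0 | -5.2 |
| same | 2 | -18.2 | -10.4 |
| same | 4 | -18.2 | -15.8 |
| 5% active, 1% placebo near zero from Day 1 | 1 | -18.7 | -51.6 |
| same | 2 | -18.9 | -54.6 |
| same | 4 | -18.7 | -52.6 |

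The near-zero subjects (one to three one-cigarette days) are taken from the quitters. At SD 2 in that scenario the between-trial SD of the estimate rises from 7.3 to 36.4 points.

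A second simulation with different assumed patterns also moved both ways. With abrupt quitters at 50% vs 20%, -15.7 became -2.7. With low counts from Day 1 in 20% vs 4% and erratic smoking otherwise, -9.8 became -28.5. With identical arms there was no bias (0.1 vs 0.3).

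**The case against.** The strongest objections, and what remains of each:

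- **The SE formula is not stated.** True: SD/√T is the natural reading, not SAP text. A Poisson-type SE would be finite for one-day and non-zero constant diaries. It would still depend on the response and would fail for all-zero and empty diaries, so the fault remains under either reading.
- **SAP 6.3 keeps dropouts in the analysis only as far as they have evaluable data.** This could be read as excluding empty diaries. It does not settle zero-variance diaries, and it conflicts with the imputation in 4.1.1 and the all-randomized set in SAP 10.
- **How often weights fail is unknown.** True. The documents give no count of such diaries, and all zeros from Day 1 would be unusual in smokers of at least 10/day.
- **The figure of about -55 rests on an assumed 5:1 imbalance.** It does, and the estimate is skewed: one re-run gave a median near -72 against a mean near -53. With 5% near-zero in both arms the means barely differ (about -18.3 and -17.2), although the between-trial SD is still near 39 points. The figure shows that a large distortion is possible; it does not forecast one.
- **The simulations omit the BMI and baseline terms.** They do. The assumed mixes also imply a per-subject SD of about 7.3/0.2449 = 30, wider than the SAP's 17.
- **The repeat across further models may refer only to the effect-modifier analyses.** That wording is ambiguous, and the conclusion does not rest on it.
- **The stakes are low.** Agreed: the analysis goes into an appendix report (SAP 6.6), no alpha is set (SAP 6.1) and no decision rule depends on it.

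**Conclusion.** The concern holds. As written, the weight is a function of the outcome, is on the wrong scale for Y, and is undefined for diaries that can occur in the all-randomized set.

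The size of the weight distortion is firm, given SE = SD/√T: a ratio of 2.3 to 50 against the abrupt quitter at 16.25/day for a steady SD of 1 to 4, and a weight of 625 for a nearly abstinent diary. The shift in the estimated difference is illustrative only. Under the assumed mix at SD 2, abrupt quitting costs 18.2 − 10.4 = 7.8 points, close to the planned ±8.3 half-width, and other patterns push the estimate the opposite way. The direction cannot be predicted from the documents.

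Severity is minor to moderate. The primary estimate is unaffected, but the study exists to supply effect estimates for later design, and this analysis would add a number that cannot be interpreted.

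**What to change.** Delete the individual 1/SE² weighting from SAP 10.1.2. Replace it with a sensitivity analysis that recomputes the endpoint with unrecorded diary days set to baseline:

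Y = 100·(N + (25 − T)·R)/(25·R)

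This is defined for every randomized subject and equals 100 at T = 0, in line with SAP 4.1.1. Example at R = 16.25: five days at baseline, five zero days, then nothing recorded (T = 10). As recorded, Y = 100 × 81.25/162.5 = 50. With baseline fill, Y = 100 × (81.25 + 243.75)/406.25 = 80.

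Weighting by T may accompany this but should not stand alone, because it gives subjects with T = 0 no weight. The SAP should state that the replacement is a conservative single imputation and that it addresses incomplete diaries, which is a different question from within-subject variability. Defining the SE and adding a rule for SE = 0 would be a smaller edit, but the weight would still depend on the response.

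The cost is SAP wording and one re-programmed secondary analysis, with no change to trial conduct. The downside is reliance on that single imputation.

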2.3. Study Population

Approximately 250 subjects who are daily cigarette smokers intending to make a quit attempt during the study will be enrolled at multiple study sites within the US. Based on the planned 2:1 (cytisine:placebo) randomization, it is expected that 200 subjects will be randomized to receive

cytisine (50 subjects at each cytisine treatment arm) and 50 subjects will be randomized to receive placebo (25 subjects per treatment schedule).

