3.5. Determination of Sample Size

The sample size was computed based on data from a previous Phase 1/2 trial and for achieving narrow confidence intervals (CI) for the primary comparison estimates in this trial.

The trial size was based on projected realization of the effect size estimate for the primary outcome based on data from a Phase 1/2 study in adult smokers. The primary outcome standard deviation from this study was found to be approximately 17. Based on this standard deviation, the estimated between-arm differences in the primary comparisons can be estimated with a 95% CI that is ± 8.3 .

The trial size will not have sensitivity for a dichotomous outcome (e.g. smoking cessation as one of the other efficacy outcomes), other than for possibly large differences. For example, if the control arm outcome is 12% (3/25 defined as successes), then the experimental arm will have a two-sided 95% CI for the probability difference that excludes zero when the success probability is 36% (8/50) or more (computation based on exact CI).

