- The placebo treatment arms (Placebo – Commercial Schedule, Placebo – tid Schedule) will be compared. If the proportion of subjects classified as a success is similar for the two placebo arms then each of the cytisine treatment arms will be compared to the pooled placebo arms.

All other sensitivity analyses for the Abstinance from Week 5 to Week 8 endpoint will be conducted by an independent statistician (). These analyses will include exploratory analyses to identify effect modifiers. The variables that will be evaluated as effect modifiers are identified [Section 10.1.2](#). The relationship between treatment arm and the proportion of subjects with abstinance will be evaluated within stratum defined by the effect modifier. For each stratum, the number (%) of subjects within each stratum with abstinance will be reported for each treatment arm. Odds ratios (1.5 mg cytisine vs. placebo, 3.0 mg cytisine vs. placebo) and their 95% CIs will also be reported. Forest plots will be used to display the stratum-specific 95% CIs.

A tipping point analysis will be performed.¹

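### SAP 10.1.2 cuts every continuous effect modifier into classes and fits no modifier-by-arm slope, which discards information on a graded effect; add the slope beside the strata

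*SAP*

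**What the plan says.** SAP 10.1.2 plans exploratory analyses, run by an independent statistician, whose aim is "to assess the homogeneity of treatment effect within strata (subgroups) defined by each potential effect-modifying variable". The candidate modifiers include age, BMI, years of smoking, cigarettes per day, number of quit attempts, CO and the baseline questionnaire scores. The list is expressly open-ended.

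Continuous modifiers are turned into classes first: "Strata for continuous effect modifiers will be defined by either logical considerations (e.g., age >65 years) or statistical criteria (e.g., quantile (median, tertile) split". No cut point is assigned to any listed variable; age over 65 is an example only. Each factor is then fitted in a "two-arm analysis of variance model with fixed effect terms for treatment arm (experimental arm, control arm), the factor, and arm-by-factor interaction", with baseline cigarettes as a covariate. For each level the output is the number of subjects, "the mean difference between treatment arms in the primary endpoint (percent of expected cigarettes smoked), and the 95% CI for the difference", shown in forest plots. The models are repeated without the baseline covariate, and with and without BMI class.

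SAP 10.2.2 uses the same variables for Week 5 to 8 abstinence. There the treatment relationship "will be evaluated within stratum defined by the effect modifier", with stratum-specific odds ratios. Neither section describes a continuous modifier-by-arm term.

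**The concern.** These variables are recorded before treatment as numbers or multi-point scores. Cutting them treats everyone within a class as alike, so a graded effect is estimated less precisely and is easier to miss. The trial is meant to supply effect estimates for later studies, and these are its only planned treatment-by-baseline interaction analyses beyond BMI class.

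The choice of cut is also left open. Fixed, median and tertile cuts are all allowed, so a reported modifier could depend on which one was used. A slope on the recorded scale does not involve that choice.

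The plan already treats one of these variables as continuous. Baseline cigarettes enters the same model as a linear covariate, yet is to be cut when examined as a modifier. Study-drug and diary compliance (SAP 9.2 and 10.1.3) are summarised both continuously and in categories.

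**Working it through.** **Inputs from the documents.** Each two-arm model has 50 active and 25 placebo subjects: "50 subjects will be randomized to receive placebo (25 subjects per treatment schedule" (SAP 2.3). For the SD: "The primary outcome standard deviation from this study was found to be approximately 17" (SAP 3.5). The illustrative placebo success rate is 12% (SAP 3.5).

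**Assumed, because the documents give no figure.** The interaction size, the shape of the modifier, the share of subjects over 65, and a two-sided 5% level as a yardstick.

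**1. The plan's own figure.** 17 × √(1/50 + 1/25) = 4.16. Multiplied by the 97.5% t quantile on 73 df this gives 8.30, matching the stated ±8.3.

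**2. Information kept by a cut.** For a normal modifier with a linear effect and a fraction p above the cut, the share kept is φ(z)²/[p(1−p)]:
- median, p = 0.50: 0.637 (= 2/π)
- top 10%: 0.342
- top 5%: 0.224

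**3. The same loss in interval width.** A slope per SD of the modifier has a 95% half-width of about 8.3. After a median split, the contrast between halves has half-width t(70) × 17 × √[2(1/25 + 1/12.5)] = 16.6. The halves of a normal modifier differ by 2 × √(2/π) = 1.596 SD on average, so this is 16.6/1.596 = 10.4 per SD, about 25% wider. Check: (8.3/10.4)² = 0.64.

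Within-stratum differences have half-widths of about 11.7 (median split) and 14.4 (tertiles).

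**4. Power by normal approximation.** At 80% continuous power the noncentrality is 1.960 + 0.842 = 2.802. Multiplying by √0.637 gives 2.236, and Φ(2.236 − 1.960) = 61%. Tertiles (2 df) give 60%. Starting from 50%, the figures are 35% and 33%.

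**5. Simulation of the SAP model.** Arm, factor, arm-by-factor and a covariate; normal modifier; 4,000 to 5,000 trials per setting (Monte Carlo error below 1 point).

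| Interaction, points of Y per SD | Continuous | Median split | Tertiles |
|---|---|---|---|
| 4 | 14–15% | 11–12% | 10% |
| 5 | 20% | 14–15% | 13% |
| 6 | 28% | 19% | 17% |
| 8.5 | 49% | 32% | 30% |
| 12 | 77% | 56% | 54% |

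The losses are about 3 to 11 points in the first three rows and 17 to 23 points in the last two (49 − 32 = 17; 77 − 54 = 23).

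**6. Tail cuts, at 12 points per SD.** Among trials where the interaction could be fitted, power is 28% for a top-10% cut and 22% for a top-5% cut. The top-5% interaction could be fitted in only 3,352 of 5,000 trials, so its overall power is 0.22 × 3,352/5,000 = 15%. If 5% of subjects were over 65, the chance of no such placebo subject is 0.95²⁵ = 28%; at 10% it is 0.90²⁵ = 7%.

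**7. The reverse case.** If the true effect is a 20-point step at the median (run without the covariate), the split has 55% power, the slope 42% and tertiles 36%.

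**8. Abstinence.** 0.12 × 25 = 3 expected placebo successes. A placebo half of 12 or 13 subjects has none with probability 0.88¹² = 22% or 0.88¹³ = 19%. An 8-subject tertile has none with probability 0.88⁸ = 36%. The sample odds ratio is then infinite or undefined.

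**The case against.** The strongest reply is that power is not what these analyses are planned around. SAP 6.1 disclaims formal hypothesis testing and sets no alpha, SAP 10.1.2 calls the work exploratory, and the stated target is the effect within strata, shown with intervals. That stands, and it is why the strata should stay. It does not remove the point, because the loss also appears as a wider interval for a graded effect (step 3).

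The second reply is that the large losses need a large interaction. Twelve points per SD is 12/17, or about 0.7 of the outcome SD. At 4 to 6 points neither analysis has more than about 28% power and the difference between them is modest. That also stands.

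A reader might go further in four ways that the documents do not support:
- **A flat cost in power for any cut.** The documents state no interaction size. The loss depends on it, on the shape of the effect and on where the cut falls, and it can change sign.
- **The 25-subject placebo arms cause the loss.** They limit absolute power, but the proportional information loss is the same at any arm size.
- **This is the plan's only look at who responds.** SAP 10.2.6 and 10.2.7 relate questionnaire scores, compliance and NMR to outcome, though not as arm interactions.
- **Age over 65 is arbitrary or fixed.** It is an example, and the sponsor's earlier study planned 18–65 and over-65 groups (Protocol 4.1). The share of older subjects here is not given.

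**Conclusion.** The point holds as a minor, optional improvement to exploratory analyses. As written, SAP 10.1.2 cuts every continuous modifier and includes no slope. Under roughly linear modification by a roughly normal modifier, a median split keeps about 64% of the interaction information. At assumed interactions of 8.5 to 12 points per SD, that costs about 17 to 23 points of power with median or tertile cuts. The cost is small for weaker interactions and larger for cuts that isolate a small tail. For a step at the median, the median split does better than the slope. No primary or key endpoint estimate is affected.

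**What to change.** In SAP 10.1.2, for each continuous or multi-point modifier, add a model with arm, the modifier on its recorded scale, arm-by-modifier and baseline cigarettes. When the modifier is itself the 7-day diary average, enter it once: SAP 6.7 defines the covariate as that same variable, and using it twice makes the model rank-deficient.

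Report the interaction slope with its 95% CI, and the cytisine–placebo difference with 95% CI at the modifier's 25th, 50th and 75th percentiles. Keep the planned strata and forest plots as a descriptive display, and fix the cut points before unblinding. Leave sex, race and site as planned.

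For abstinence (SAP 10.2.2), a continuous logistic interaction should be optional. With about 3 expected placebo successes its benefit has not been shown.

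The cost is SAP wording and a few lines of code; no new data are needed and no planned output is lost. The one downside is that the slope assumes an approximately linear trend, which the retained strata help to check.
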